Appendix A. Total Bilirubin Table for Term and Preterm Neonates

PARAMETER	GRADE 1 MILD	GRADE 2 MODERATE	GRADE 3 SEVERE	GRADE 4 POTENTIALLY LIFE-THREATENING
Total Bilirubin ¹⁶ , High (mg/dL; µmol/L) ¹⁷				
Term Neonate ¹⁸				
< 24 hours of age	4 to < 7 68.4 to < 119.7	7 to < 10 119.7 to < 171	10 to < 17 171 to < 290.7	≥ 17 ≥ 290.7
24 to < 48 hours of age	5 to < 8 85.5 to < 136.8	8 to < 12 136.8 to < 205.2	12 to < 19 205.2 to < 324.9	≥ 19 ≥ 324.9
48 to < 72 hours of age	8.5 to < 13 145.35 to < 222.3	13 to < 15 222.3 to < 256.5	15 to < 22 256.5 to < 376.2	≥ 22 ≥ 376.2
72 hours to < 7 days of age	11 to < 16 188.1 to < 273.6	16 to < 18 273.6 to < 307.8	18 to < 24 307.8 to < 410.4	≥ 24 ≥ 410.4
7 to 28 days of age (breast feeding)	5 to < 10 85.5 to < 171	10 to < 20 171 to < 342	20 to < 25 342 to < 427.5	≥ 25 ≥ 427.5

¹⁶ Severity grading for total bilirubin in neonates is complex because of rapidly changing total bilirubin normal ranges in the first week of life followed by the benign phenomenon of breast milk jaundice after the first week of life. Severity grading in this appendix corresponds approximately to cut-offs for indications for phototherapy at grade 3 and for exchange transfusion at grade 4.

¹⁷ A laboratory value of 1 mg/dL is equivalent to 17.1 µmol/L.

¹⁸ Definitions: Term is defined as ≥ 37 weeks gestational age; near-term, as ≥ 35 weeks gestational age; preterm, as < 35 weeks gestational age; and neonate, as 0 to 28 days of age.

7 to 28 days of age (not breast feeding)	1.1 to < 1.6 x ULN	1.6 to < 2.6 x ULN	2.6 to < 5.0 x ULN	≥ 5.0 x ULN
Preterm Neonate 35 to < 37 weeks gestational age	20 Same as for Total Bilirubin, High, Term Neonate (based on days of age).	Same as for Total Bilirubin, High, Term Neonate (based on days of age).	Same as for Total Bilirubin, High, Term Neonate (based on days of age).	Same as for Total Bilirubin, High, Term Neonate (based on days of age).
32 to < 35 weeks gestational age and < 7 days of age	NA	NA	10 to < 14 171 to < 239.4	≥ 14 ≥ 239.4
28 to < 32 weeks gestational age and < 7 days of age	NA	NA	6 to < 10 102.6 to < 171	≥ 10 ≥ 171
< 28 weeks gestational age and < 7 days of age	NA	NA	5 to < 8 85.5 to < 136.8	≥ 8 ≥ 136.8
7 to 28 days of age (breast feeding)	5 to < 10 85.5 to < 171	10 to < 20 171 to < 342	20 to < 25 342 to < 427.5	≥ 25 ≥ 427.5
7 to 28 days of age (not breast feeding)	1.1 to < 1.6 x ULN	1.6 to < 2.6 x ULN	2.6 to < 5.0 x ULN	≥ 5.0 x ULN

### Revision history

Revision	Date	Section/Page	Changes Made -- Reasons for the Change
2.0	9/14/20	Throughout	Updated to match Protocol version 3
2.0	9/14/20	Sections 2 & 3	Details added about statistical methods and missing data handling

## INTRODUCTION

This statistical analysis plan (SAP) is a comprehensive and detailed description of the strategy, rationale, and statistical techniques that will be used in the study.

## 1 STUDY DETAILS

### 1.1 Study design

This phase 2 randomized, single-blind study intends to evaluate the efficacy of a single dose of peginterferon lambda-1a in outpatients with mild COVID-19 compared with placebo in reducing the duration of shedding of SARS-CoV-2 virus.

One hundred and twenty (60 per arm) enrolled patients will be randomized in a 1:1 fashion. Thus, there will be two arms: (1) the control arm, comprised of placebo in addition to standard supportive care and (2) the treatment arm, comprised of a single dose of peginterferon lambda-1a in addition to standard supportive care. An interim analysis for safety and overwhelming efficacy will be performed once 50% of patients have 24 hours of follow-up complete.

The primary analysis is based on intent-to-treat principles in that all patients who are randomized to study arm are included in the analysis, where cessation of shedding is assessed according to randomized study arm. The secondary analysis of adverse events (AE) are assessed according to dose received.

### 1.2 Primary endpoint

The primary endpoint is time until cessation of oral shedding of SARS-CoV-2 virus, defined as the time in days from randomization to the first of two negative oropharyngeal tests. Patients who do not experience the endpoint will be censored at 28 days after randomization (end of study) or at the time of premature withdrawal.

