5. CRITERIA FOR EVALUATION

5.1. Primary efficacy endpoint

- Time to first of two consecutive negative oropharyngeal tests for SARS-CoV-2 by qRT-PCR.

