9 SUBJECT MANAGEMENT

9.1 Subject Follow-up

9.1.1. In home assessments.

Participants will complete an at-home symptom questionnaire by REDcap on each day of follow-up through day 28, including in-home assessments of temperature and O2 saturation. These assessments will be reviewed daily by a clinical research coordinator, and patients will be telephoned by a physician if they report an elevated temperature, diminished O2 sat (<94%), or signs/symptoms of respiratory or cardiopulmonary distress (e.g. shortness of breath, dyspnea on exertion). On each day through day 28, patients will also be instructed to collect an anterior nare swab in a pre-labeled container and to store these specimens in a refrigerator at 2°C to 8°C, and to bring these in to their next scheduled appointment. Prior to the optional follow up visits at months 4, 7 and 10, participants will complete an at-home symptom questionnaire and will be asked to collect a stool specimen to bring to their next scheduled appointment.

9.1.2. Follow-up in-clinic assessments.

[figure not shown]
Participants will be seen at follow-up visits at Day 1±1, 3±1, 5±1, 7±1, 10±1, 14±1, 21±1, and 28±1. At each visit, a subjective medical history will be performed, including assessments for use of any concomitant medications. Vital signs will be obtained (temperature, blood pressure, pulse rate per minute, breath rate per minute and oxygen saturation), and oropharyngeal and anterior nare swabs will be collected. Participants will also submit at-home collected anterior nare swab specimens for evaluation. Clinical laboratory measurements will be performed at days 5±1 and 14±1 to assess for safety, with additional clinical laboratory assessments performed as needed for clinical follow-up and/or patient management. Additionally, ~25 mL peripheral blood will be collected from study participants at enrollment and at Days 5±1, 14±1, and 28±1 for processing and cryopreservation into a specimen biobank. Safety and tolerability of Lambda will be assessed by adverse event (AE) monitoring, vital signs assessment and clinical laboratory tests. Patients will reach the end of study at day 28±1 of follow-up. Optional long-term follow up visits will be scheduled 4, 7, and 10 months post-enrollment. The window of ±3 weeks is allowed for these long term follow up visits.

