## 3 HANDLING OF MISSING AND CENSORED DATA

All efforts will be made to minimize instances of missing data. However, we expect some missing data will occur. Our analyses will assume data are missing at random. For the primary endpoint of time to shedding cessation, any participant who drops out prior to having two consecutive negative tests will be censored at their last positive test. Participants who have no post-randomization test results available or a single test result that is negative will be censored at day 1. Similarly, participants will be right censored for the time to symptom resolution or progression at the time when their last symptom questionnaire is completed. Participants who are asymptomatic at screening and never report symptoms thereafter will be considered to have met symptom resolution at study Day 1. For other missing data, we will use multiple imputation-based analyses. This approach will be applied to any analysis involving endpoints or key

variables where any missing data occurs in order to adhere to the ITT principle. Sensitivity to assumptions regarding missingness will be addressed through sensitivity analyses.

If more than 5% of participants do not have the time of shedding cessation observed (i.e. they are right-censored), we will perform a sensitivity analysis to evaluate the robustness of our findings to missing data assumptions. In the sensitivity analysis, among those missing timing of shedding cessation, we will assume varying proportions (e.g. 25%, 50%) of participants in each arm who would have ceased shedding by Day 28. The proportions will differ by arm so we can evaluate whether our findings stand if it were true that people who dropped out stopped shedding earlier in the placebo arm vs the active arm.

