### 4.2 Determination of sample size

We assume that the mean duration of virologic shedding in individuals receiving standard of care is 14 days, with a standard deviation of 4 days.

Assuming 1:1 randomization and the use of a two-sided log rank test at the alpha=0.04999 level of significance for the final analysis, 79 events will provide 80% power to detect a hazard ratio of 2.03. This leaves alpha=0.00001 to check for overwhelming efficacy after 50% of participants have completed 24 hours of follow-up. Assuming the control and treatment arm median cessation of shedding is 14 and 7 days, respectively, a two-month accrual period, a two-week follow-up period after randomization of the last patient, and a drop out of 10% in the control arm, it is estimated that the total sample size required to achieve 79 events is 120 (60 patients in each arm).

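### SAP 1.2 leaves *consecutive* out of the primary endpoint, contrary to Protocol 5.1 and SAP 3, and censors drop-outs at a different time from SAP 3

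*SAP*

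**What the plan says.** **Event.** Protocol 5.1 defines the primary endpoint as "Time to first of two consecutive negative oropharyngeal tests for SARS-CoV-2 by qRT-PCR". SAP 1.2 has it "defined as the time in days from randomization to the first of two negative oropharyngeal tests", without the word *consecutive*. SAP 3 brings the word back when it describes drop-outs.

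**Censoring.** SAP 1.2 states that participants without the endpoint "will be censored at 28 days after randomization (end of study) or at the time of premature withdrawal". SAP 3 states that "any participant who drops out prior to having two consecutive negative tests will be censored at their last positive test", and adds: "Participants who have no post-randomization test results available or a single test result that is negative will be censored at day 1". Protocol 5.1 and 12.3 and SAP 2.3 give no censoring rule, and nothing says which SAP section governs.

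**Schedule.** Protocol 9.1.2 fixes when oropharyngeal swabs are taken: "Participants will be seen at follow-up visits at Day 1±1, 3±1, 5±1, 7±1, 10±1, 14±1, 21±1, and 28±1".

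**The concern.** SAP 1.2 is where a programmer looks for the derivation of the primary variable. If it is coded as written, any participant with an isolated negative during shedding can get an earlier event time, or an event where the protocol sees none.

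If false negatives can occur throughout shedding, the arm that sheds longer has more swabs at risk. The error therefore pulls the hazard ratio for cessation toward 1. The same event time feeds the interim efficacy test (SAP 5), the subgroup and effect-modification analyses (SAP 2.7), and the count of censored participants that triggers the sensitivity analysis in SAP 3.

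The censoring conflict is separate, and restoring *consecutive* does not remove it. Choosing between either pair of rules after outcomes are known would invite the charge of a data-driven choice.

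**Working it through.** **1. Event rules on the visit schedule** (days 1, 3, 5, 7, 10, 14, 21, 28; P positive, N negative)

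| Results in visit order | Protocol 5.1 and SAP 3 | SAP 1.2 read literally |
|---|---|---|
| P P N P P P N N | event at day 21 | event at day 5 |
| P N P P P P P N | no event, censored at day 28 | event at day 3 |

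A single negative with no other is not an event under either rule.

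**2. Censoring rules**

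| Participant | SAP 1.2 | SAP 3 |
|---|---|---|
| Positive days 1, 3, 5; negative day 7; withdrawn day 10 | day 10 | day 5 |
| One negative result only; withdrawn day 14 | day 14 | day 1 |
| Completes day 28 without the endpoint | day 28 | no conflict |

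**3. Size of the event conflict.** The plan states no figure on this point to reproduce.

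- *Inputs from SAP 4.2:* medians 14 and 7 days, 60 per arm, two-sided alpha 0.04999.
- *Assumptions:* exponential clearance, 10% drop-out in both arms spread evenly over 28 days (the plan states 10% for control only), swabs on the nominal days, and the false-negative rate and its timing.
- *Method:* Cox model with Efron ties, 1,500 trials per setting. The Monte Carlo standard error of power is about 0.01.

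Both columns censor at withdrawal, so only the event rule differs.

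| False negatives per swab | HR, consecutive / literal | Power, consecutive / literal | Participants changed |
|---|---|---|---|
| None | 2.00 / 2.00 | 0.877 / 0.877 | none |
| Constant 5% | 1.97 / 1.86 | 0.883 / 0.837 | 10% |
| Constant 10% | 1.92 / 1.70 | 0.877 / 0.725 | 18.5% |
| Constant 20% | 1.77 / 1.46 | 0.785 / 0.486 | 30% |
| Average 10%, rising toward clearance | 1.98 / 1.91 | 0.895 / 0.864 | 11% |
| 5% to 30%, only in the last 4 days before clearance | at 30%: 1.99 / 1.99 | differs by under 0.5 points | 1% to 6% |

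At a constant 10%, 20% of control and 17% of treated participants change. Repeat runs of that setting gave power of 0.86 against 0.71 to 0.73. One repeat run with no false negatives gave 0.91 instead of 0.877, so absolute power carries a few points of noise. The contrast between the two rules is stable.

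**4. Why power starts near 0.88 and not 0.80.** SAP 4.2 says that "79 events will provide 80% power to detect a hazard ratio of 2.03". By Schoenfeld's formula, power = Φ(½ × √79 × ln 2.03 − 1.96) = Φ(4.444 × 0.708 − 1.96) = Φ(1.19) ≈ 0.88. A starting power of 0.88 is therefore in line with the planned number of events. The 80% claim is a separate matter, and this point does not rest on it.

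**5. Size of the censoring conflict.** With the consecutive rule and no false negatives, the HR is 2.003 censoring at withdrawal and 2.009 under SAP 3: 2.009 / 2.003 = 1.003, a shift of 0.3%. Power is 0.877 and 0.881. About 6% of participants get a different time.

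**The case against.** **It is a dropped word.** Protocol 5.1 and SAP 3 agree, no passage argues for non-consecutive negatives, and a negative followed by positives is hardly cessation. A careful programmer would follow the other two sections. This stands as a reading of intent. The revision note, "Updated to match Protocol version 3", points the same way but weakly, because the version of the protocol at hand cannot be confirmed. None of it changes what the defining section says.

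**The power loss depends on assumptions.** The documents give neither a false-negative rate nor its timing, and the large losses need errors throughout shedding. The clearance distribution matters too. SAP 4.2 also assumes a mean of 14 and SD of 4 days, whereas an exponential with median 14 has SD 14 / ln 2 = 20.2 days. With gamma shedding times (means 14 and 7, SD 4 in both arms), power is 1.00 against 0.995 at a constant 10%, and 1.00 against 0.845 at 20%. This stands: the loss of about 15 power points at 10% is specific to the exponential model. The distortion of the estimate is not. Under the gamma model at 10% the HR falls from about 3.6 to 2.4 (3.76 to 2.54 in a second run), and 24% of participants change.

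**The censoring conflict is immaterial, and the choice of rule belongs to the sponsor.** Numerically it is immaterial when drop-out is unrelated to shedding, as simulated. Either rule could be defended; what is needed is one. A further remark is that SAP 3 does not limit its day-1 rule to drop-outs. That has no practical effect, since a participant with at most one result can hardly have completed follow-up.

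**Conclusion.** The concern holds. SAP 1.2 states an event rule that contradicts Protocol 5.1 and SAP 3, and a drop-out censoring rule that contradicts SAP 3. It should be corrected before database lock.

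The event conflict matters only if SAP 1.2 is coded literally and isolated negatives occur during shedding. Its effect then runs from none (no false negatives) to 30% of participants changed and an HR of 1.46 instead of 1.77 (constant 20%, exponential clearance). The direction, toward an HR of 1, is the same under both distributions when errors occur throughout shedding. The power figures are illustrative and rest on the assumed error rate, its timing and the clearance distribution. The censoring conflict is a matter of consistency, with an effect on the HR of under 0.5%.

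**What to change.** Make two edits to SAP 1.2.

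1. Insert *consecutive* before *negative* in the endpoint definition, so that it matches Protocol 5.1 and SAP 3.
2. Replace the censoring sentence with one such as: *Drop-outs without the endpoint are censored as set out in Section 3 (last positive test, or day 1 where the only result is one negative or there is none); those who complete follow-up without it are censored at day 28.*

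SAP 3 is the natural source for the drop-out rule: it is the dedicated and more detailed section, and the last positive test is the last time shedding was observed. If the sponsor prefers censoring at withdrawal, SAP 3 should be changed instead, so that one rule remains.

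The cost is two sentences of SAP text. Visits, data collection and sample size are unaffected.

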### 1.3 Secondary endpoints

Secondary endpoints include the following:

- Time until resolution of all symptoms;
- SARS-CoV-2 viral load over time in oropharyngeal tests;
- SARS-CoV-2 viral load area under the curve in oropharyngeal tests through Day 14;
- Number of emergency department visits or hospitalizations within 28 days of treatment.

### 1.4 Exploratory endpoints

Exploratory endpoints include the following:

- Time until sustained symptom resolution;
- Time until resolution of respiratory symptoms (cough, sore throat, runny nose, chest pain, and shortness of breath);

- Time until resolution of systemic and respiratory symptoms (headache, fever/chills, muscle/joint pain, fatigue and respiratory symptoms described above);
- Time until disease progression;
- SARS-CoV-2 infection-free by negative RT PCR testing results from nasal swabs on Days 5, 7, 10, and 14;
- SARS-CoV-2 infection-free by negative RT PCR testing results from oropharyngeal swabs on Days 5, 7, 10, and 14;
- SARS-CoV-2 viral load over time in nasal tests;
- SARS-CoV-2 viral load area under the curve in nasal tests through Day 14;
- Seroconversion by Day 28 (presence of IgG antibodies to SARS-CoV-2 Spike Receptor Binding Domain, as measured by ELISA);
- Cellular immune responses;
- Host genetics.

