9.4 Biobanking/Immune phenotyping

We will biobank longitudinal samples collected from patients enrolled in this trial. This will allow for ongoing studies to define the dynamics of the host immune response to COVID-19, with the eventual goal of gaining insight into mechanisms by which control or prevention can be achieved. For biobanking activities, samples will be collected at enrolment, day 5 ± 1 , day 14 ± 1 , and day 28 ± 1 post-randomization, with optional additional biobanking at 4, 7, and 10 months post-randomization (Fig 4). The window of ± 3 weeks is allowed for these long term follow up visits. Stool will be collected as above and biobanked for microbiome assessments.

At the time of blood draw, one 2.5 ml PaxGene tube and two 10 ml CPT (or green-top heparin) tubes will be collected for biobanking and brought to the BSL2+ research lab in Grant S146b. This whole blood then be stored in either stored in specific fixatives, used directly to assess innate immune phenotype and/or the immune response to toll like receptor stimulation, and/or separated into plasma and peripheral blood mononuclear cells (PBMC) using a Ficoll gradient, following standard protocols. All samples will have unique labels with barcodes and unique study identifier. Specimens will be logged into the Stanford Biobank through the OpenSpecimen database tracking system. Plasma will be stored at -80°C for future immunologic and/or pharmacokinetic studies, which may include measurement of levels of cytokines, antibodies, and other features related to the host immune response. PBMCs will be stored in liquid nitrogen to maintain viability, and will be evaluated using flow cytometry, RT-PCR, RNA sequencing, and other assays to assess the host immune response.

In a subset of patients, we will consider a finger stick blood sample at day 14 and/or 28 to collect blood on a dry blood spot to validate performance characteristics of a serologic assay in comparison to venipuncture.

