# 2 ANALYSIS PLAN

## 2.1 Analysis populations

The intent-to-treat (ITT) population will include all randomized patients. Patients will be analyzed according to their assigned treatment arm. All efficacy analyses will be completed in the ITT population.

The as-treated population will include all randomized patients. Patients will be analyzed according to the treatment actually received.

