## 2.5 Exploratory efficacy analyses

An alternative definition of the secondary endpoint of symptom resolution will be considered in an exploratory analysis. We will evaluate time to sustained symptom resolution, defined as time from randomization until the first day in which no symptoms are reported and are not reported for the duration of the study. The analysis of time to sustained symptom resolution will follow the methods described for the secondary endpoint evaluation symptom resolution in the previous section. Time to symptom resolution based on symptom subsets (i.e. respiratory, systemic) will be similarly analyzed, additionally excluding participants who did not report symptoms from the specified subset at screening.

Time to disease progression will be defined as the time from randomization until the first day of a two point or more increase in either cough or shortness of breath persisting for at least 48 hours or an increase to a score of 4 or 5, or first day of admission to the emergency department, hospitalization, or death. Analysis and reporting of results will be done following methods detailed for time to symptom resolution.

Freedom from SARS-CoV-2 infection by oropharyngeal and nasal swabs at Day 5, 7, 10, and 14 will be modeled using a multivariable logistic regression model adjusted for age and sex. The odds ratio will be presented along with its 95% confidence interval.

Similar approaches to those used for evaluating SARS-CoV-2 viral load in oropharyngeal tests over time and AUC will be used to evaluate viral load in nasal tests.

Correlation between virology and symptomology will be characterized by evaluating the relationship between CT values obtained from the oropharyngeal tests and each symptom through two main approaches. For symptoms graded on an ordinal scale, we will calculate a Spearman correlation and assess significance with a Z-test. For variables that capture presence of a symptom, differences in the median CT values by presence or absence of the symptom will be presented and assessed via a Wilcoxon rank sum test.

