## 2.7 Effect modification, subgroup, and sensitivity analyses

A subgroup analysis will be performed for the primary endpoint using only patients who present with symptoms at baseline.

A statistical interaction term between treatment arm and the following baseline characteristics will be added to the Cox proportional hazards model to test for effect modification.

- 1) CT value < 30 from the baseline OP swab,
- 2) presence of antibodies as defined by presence of IgG antibodies to SARS-CoV-2 Spike Receptor Binding Domain (RBD) at baseline, as measured by ELISA. Samples are considered seropositive against RBD if their absorbance value was greater than the mean of plus four standard deviation (SD) of all negative controls (n=130),
- 3) number of risk factors or predictors for severe disease present at baseline (temp 99.5+, cough, or shortness of breath present at randomization [symptoms count as a single risk factor], age  $\geq$  60, male sex, Black race, Hispanic ethnicity, BMI  $\geq$  30, and lab values of baseline lymphocyte counts <1000 and baseline ALT  $\geq$  94),
- 4) age  $\geq$  50,
- 5) sex

A Wald test performed at the alpha = 0.05 level of significance will be used to test whether the effect modification is statistically significant. The sensitivity and effect modification analyses will be performed in other key endpoints as well.

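### Seroconversion by Day 28 is defined as IgG presence alone, so participants already IgG-positive at Day 0 count as converters and the reported rate is inflated.

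*SAP*

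**What the plan says.** SAP 1.4 (Exploratory endpoints) lists "Seroconversion by Day 28 (presence of IgG antibodies to SARS-CoV-2 Spike Receptor Binding Domain, as measured by ELISA" and adds nothing about the baseline sample. The protocol does not list seroconversion as an endpoint.

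SAP 2.7 names as an effect modifier the "presence of antibodies as defined by presence of IgG antibodies to SARS-CoV-2 Spike Receptor Binding Domain (RBD) at baseline, as measured by ELISA" and gives a positivity cut-off based on 130 negative controls. Its use is as follows: "A statistical interaction term between treatment arm and the following baseline characteristics will be added to the Cox proportional hazards model". The section closes with "The sensitivity and effect modification analyses will be performed in other key endpoints as well" and does not say which endpoints those are.

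On the analysis set, SAP 2.1 says "All efficacy analyses will be completed in the ITT population". No baseline-seronegative subset is defined. SAP 2.5 (Exploratory efficacy analyses) gives no model, test or analysis set for seroconversion.

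On sampling, Protocol 9.4 says "For biobanking activities, samples will be collected at enrolment", with further draws at Days 5, 14 and 28.

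**The concern.** Seroconversion means a change from negative to positive. The definition in brackets asks only whether antibody is present. Someone already positive at Day 0 cannot convert, yet meets the definition.

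Such participants are to be expected. Protocol 6.2 and 6.3 contain no criterion on serostatus and no limit on time since symptom onset; a symptomatic patient needs only a recent positive molecular test. SAP 2.7 would have no reason to plan an interaction with baseline IgG if everyone were expected to be negative.

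Two things are at stake: the conversion rate reported for each arm and, if the arms are compared, the size and meaning of the difference. Two analysts could also produce different denominators from the same text, one following the label and the other the definition.

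**Working it through.** The plan states no rate, effect size or power for this endpoint, so there is no figure of its own to reproduce. The check has two parts.

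**1. Does any other section supply the missing condition?**

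- SAP 2.1 points to all randomized patients.
- SAP 2.5 does not mention seroconversion. It does state a baseline restriction where one is wanted: the symptom-subset endpoints are analysed "additionally excluding participants who did not report symptoms from the specified subset at screening". Nothing similar appears for serology.
- SAP 2.7 uses baseline IgG as an interaction term and not to define who is at risk of converting.

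No section supplies it.

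**2. What does the literal rule do to the numbers?**

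Let s be the share IgG-positive at baseline, assumed to be still counted positive by Day 28. Let c and t be the true conversion rates among baseline-negatives in the two arms. With s equal in both arms:

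- reported rates: s + (1 − s)c and s + (1 − s)t
- reported risk difference: (1 − s)(c − t)

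All values of s, c and t below are assumptions. With c = 95% and t = 80% (true difference 15 points):

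| s | Reported, higher arm | Reported, lower arm | Difference |
|---|---|---|---|
| 10% | 0.10 + 0.90 × 0.95 = 95.5% | 0.10 + 0.90 × 0.80 = 82.0% | 13.5 points |
| 30% | 0.30 + 0.70 × 0.95 = 96.5% | 0.30 + 0.70 × 0.80 = 86.0% | 10.5 points |
| 50% | 0.50 + 0.50 × 0.95 = 97.5% | 0.50 + 0.50 × 0.80 = 90.0% | 7.5 points |

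Power compares the literal rule (n = 60 per arm, from SAP 1.1) with restriction to baseline-negatives (n = 60(1 − s) per arm). It uses the two-proportion normal approximation at two-sided alpha 0.05, where d is the risk difference, p1 and p2 are the two rates and p̄ is their mean:

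power = Φ{[|d| − 1.96√(2p̄(1 − p̄)/n)] / √([p1(1 − p1) + p2(1 − p2)]/n)}

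With c = 80% and t = 60%, the restricted analysis keeps a risk difference of 0.20 and an odds ratio of 0.375 throughout:

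| s | Literal rule: risk difference | Literal rule: odds ratio | Literal rule: power | Restricted: n per arm | Restricted: power |
|---|---|---|---|---|---|
| 0 | 0.20 | 0.375 | 67.0% | 60 | 67.0% |
| 10% | 0.18 | 0.390 | 60.5% | 54 | 62.4% |
| 20% | 0.16 | 0.405 | 53.7% | 48 | 57.2% |
| 40% | 0.12 | 0.432 | 40.0% | 36 | 45.6% |
| 50% | 0.10 | 0.444 | 33.3% | 30 | 39.1% |

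Across this pair and two others (90% vs 70%, 70% vs 50%), restriction gains about 1 to 7 points of power for s between 10% and 50%. The odds ratio moves much less than the risk difference.

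**Chance imbalance.** SAP 1.5 stratifies randomization by age and sex only. With 60 per arm, the standard deviation of the between-arm difference in s is √(2s(1 − s)/60), which is 0.073 at s = 20% and 0.089 at s = 40%. If treatment has no effect and the common true rate is p, an imbalance Δs produces a spurious risk difference of Δs(1 − p). At an assumed p = 80%, one standard deviation gives 0.073 × 0.20 = 0.015 or 0.089 × 0.20 = 0.018, in either direction.

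**The case against.** **The word already implies a change.** The brackets may only name the marker and assay, leaving the usual meaning of seroconversion to supply the baseline condition. That may be what was intended. But the brackets are the only operational definition given, and on this reading the label and the definition still disagree.

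**IgG positivity in all randomized participants is a valid randomized comparison.** This stands. It is not a biased estimate of its own quantity and it fits SAP 2.1. It answers a different question from the one the name announces, which is why it should be reported separately under its own name.

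**SAP 2.7 may cover it.** The interaction with baseline antibody might be extended to this endpoint, and the seronegative stratum could then be read off. But the extension is to unnamed key endpoints, and an exploratory endpoint may not be one of them. Baseline-positives all meet the endpoint by definition, so their stratum says nothing about treatment and the headline rate stays inflated.

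**Stronger readings go too far.**

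- A reader might infer that the plan commits to a biased treatment comparison. SAP 2.5 specifies no between-arm analysis of seroconversion, so the effect on a difference is conditional on one being made.
- A reader might infer that the trial would give the wrong answer to a stated question about interferon and antibody response. No such question is stated. The protocol objectives do not mention antibodies, and Protocol 9.4 gives the aim of biobanking as describing the host immune response to COVID-19.
- A reader might infer that the difference always moves toward zero. That holds when s is balanced; in a single trial of this size it need not be.

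**Conclusion.** The point holds as a defect in a definition. Followed literally, SAP 1.4 scores baseline-positive participants as converters, and nothing elsewhere corrects it. Inflation of the reported rate follows directly whenever s is above zero and the true rate is below 100%. Shrinkage of a risk difference by the factor (1 − s) needs two further conditions: that the arms are compared, and that s is balanced.

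The size cannot be derived from the documents, because they give no baseline share and no conversion rates. Every figure above is an illustration and assumes that baseline-positives remain positive. The main loss is in what the estimate means; the loss of power is modest. The consequence is minor: this is one of eleven exploratory endpoints, with no decision rule attached.

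**What to change.** In SAP 1.4, define seroconversion as IgG-negative at Day 0 and IgG-positive at a later sample up to Day 28, using the cut-off already given in SAP 2.7. In SAP 2.5:

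- name baseline-negative participants as the analysis set;
- report overall Day 28 seropositivity in all randomized participants as a separate quantity, and the number of baseline-positives by arm;
- state whether the arms will be compared and by what model;
- say how a missing baseline serology result is handled.

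Because the subset is defined on blood taken at the intake visit (Protocol 6.6), before treatment, the randomized comparison within it is preserved.

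The cost is SAP wording. The blood draws are already scheduled, and baseline IgG is already needed for SAP 2.7. The downside is fewer participants: at an assumed 10%, 30% or 50% baseline-positive, 60(1 − s) leaves 54, 42 or 30 per arm.
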